9.1.2.2 Follow-Up Period

All subjects, regardless of whether they complete all 24 months of treatment or discontinue study drug prematurely, will complete 2 post-treatment Follow-Up Visits; one 4 weeks after the last dose of study drug and a second 12 weeks after the last dose of study drug (Visit 14 and Visit 15 respectively). If clinically indicated, more frequent safety assessments can be made as unscheduled (UNS) assessments or visits during the post-treatment follow-up period.

In some cases, UNS visits will be needed to follow-up on safety or other findings, and the related assessments (outlined in the Schedule of Assessments) will depend on the reason for the UNS visit, and will be decided at the discretion of the investigator.

9.1.3 Extension Phase

An open-label Extension Phase will be available for subjects who complete the full 24 months of treatment in the Core study. The start of the open-label Extension Phase will require prior approval of an amendment from applicable Health Authorities and will continue until commercial availability of elenbecestat (E2609), or until a positive risk-benefit assessment in this indication is not demonstrated. (revised per Amendment 03) Full details of the Extension Phase will be available in a future protocol amendment.

9.1.4 End of Study

The end of the study for the double-blind Randomization Phase will be the date of the last study visit (Visit 15) for the last subject in the double-blind Randomization Phase. (revised per Amendment 03)

9.2 Discussion of Study Design, Including Choice of Control Groups

9.2.1 Overview

This study is a multicenter, multiple-dose, double-blind, placebo-controlled, parallel-group study in subjects with EAD including MCI due to AD and the early stages of mild AD, aiming to randomize a total of 1330 subjects across 2 treatment groups, (placebo, 50 mg per day elenbecestat [E2609]) for 24 months. The maximum estimated duration for each subject on study is anticipated to be approximately 29 months (ie, 2-month Prerandomization Phase, followed by 24 months of treatment and a 3-month Follow-Up Phase).

As currently there is no cure for AD, there is no active or positive control for this study as at this time, no known way of slowing the progression of this disease, and no approved treatment available to reverse the deterioration of AD.

The primary endpoint of this study is to evaluate the effects of elenbecestat (E2609) compared to placebo on the CDR-SB score. This endpoint is widely used in AD trials as a global measure of disease progression. The instrument is rated after a semi-structured interview with the subject and a study partner, and does not directly rely on psychometric tests, thus avoiding learning effects. One important factor associated with the use of the CDR-SB is that it is designed to incorporate cognitive and functional components; changes in the CDR-SB score reflect changes in both components. The clinical researcher separately interviews the subject and a study partner in order to assess changes in the subject's performance relative to their premorbid performance on 6 domains: memory, orientation, judgment and problem solving; community affairs, home and hobbies, and personal care. Each domain is scored as 0 (none), 0.5 (questionable) except for personal care, 1.0 (mild), 2.0 (moderate), or 3 (severe). Two overall scores can be derived – a calculated global score using a standardized algorithm and a cumulative score summing the boxes. The cumulative score or CDR-SB is a well-described, validated, and reliable measure of change through the course of AD and has been proposed as a suitable single outcome measure for AD trials in dementia and pre-dementia populations.

Additional secondary endpoints of the study will evaluate the effects of elenbecestat (E2609) compared to placebo on time to disease progression, time to conversion to dementia, the ADAS-cog₁₄ (including a separate endpoint for the immediate recall and delayed recall subtests), MMSE, and FAQ at 24 months. These scales are also widely used and well recognized instruments in AD trials. (revised per Amendment 01)

Additional important biomarker endpoints will evaluate the AD modifying properties of elenbecestat (E2609) by assessing several human AD biomarkers. (revised per Amendment 01) Of note, there is no widely recognized consensus over the utilization of a single AD biomarker as a measure of disease modification. Therefore, it is proposed that several biomarkers will be utilized during this study without a specific hierarchical approach.

The proposed exploratory biomarkers for this study are aimed at evaluating the effects of elenbecestat (E2609) on disease progression and neurodegenerative (NDG) changes correlating these with clinical benefit. An additional analysis will evaluate whether

inhibition of amyloid production by elenbecestat (E2609) has downstream effects on neurodegeneration (as measured by CSF and brain tau levels that are thought to be associated with neurofibrillary pathology), especially in the EAD population. (revised per Amendment 04)

Randomization and stratification will be used in this study to avoid bias in the assignment of subjects to treatment, to increase the likelihood that known and unknown subject attributes (eg, demographics and baseline characteristics) are balanced across treatment groups, and to ensure the validity of statistical comparisons across treatment groups. Blinding to treatment will be used to reduce potential bias during data collection and evaluation of endpoints.

Rationale for the selection of doses used in the study is provided in [Section 9.4.4](#).

9.2.2 Rationale for Study Population

This study will enroll subjects with EAD including MCI due to AD and the early stages of mild AD. It is considered that this population is the most likely to benefit from the administration of a BACE1 inhibitor such as elenbecestat (E2609). This is because as AD progresses to the clinical diagnosis of dementia and more severe stages of the disease with the loss of functional capabilities, the amyloid load in the brain has already reached a plateau and significant neurodegeneration has occurred ([Jack et al., 2011](#)). There is a growing consensus within the AD field that it may be necessary to initiate disease-modifying treatments earlier, before the onset of clinical dementia ([Aisen et al., 2010](#)). As a consequence, attempts to slow disease progression with elenbecestat (E2609) are most likely to succeed at an earlier stage at which there is limited neurodegeneration; therefore, the selected population for this study is subjects with EAD including MCI due to AD and the early stages of mild AD.

Subjects who do not meet all of the inclusion criteria or who meet any of the exclusion criteria will not be eligible to receive study drug.

9.2.3 Rationale for Clinical Endpoints

The CDR is a clinical global rating scale requiring the interviewing of both the subject and a study partner who knows and has contact with the subject. The CDR is a clinician directed assessment of both cognition and function, and is intended to capture the state and therefore the disease stage of the individual. The CDR has been proposed as an acceptable approach for following disease progression and confirming treatment effects in AD. The cumulative score or CDR-SB is a well-described, validated, and reliable measure of change through the course of AD and has been proposed as a suitable single outcome measure for AD trials in dementia and pre-dementia populations ([FDA 2013 AD Guidelines](#), [EMA 2016 AD Guidelines](#)).

The ADAS-Cog is the most widely used cognitive scale in AD clinical studies ([Rosen, et al., 1984](#)). The 14-item version will be used in the present study since it is considered more sensitive for less impaired populations such as MCI/Prodromal and mild AD subjects

(Fleisher, et al., 2007). Furthermore, a separate endpoint for the ADAS-cog₁₄ immediate recall and delayed recall subtests is included. (revised per Amendment 01)

The MMSE is a cognitive instrument commonly used for screening purposes, for staging of disease severity and is often measured longitudinally in AD clinical studies to follow disease progression and treatment effects (Folstein, et al., 1975).

The FAQ collects information on 10 items concerned with performing daily tasks necessary for independent living. The FAQ is considered as a better indicator of clinical meaningfulness than cognitive change as it reflects the subject's functional state and should correlate well with AD progression.

The ISLT is sensitive to memory impairment that characterizes both AD and MCI (Lim, et al., 2012a). In MCI subjects, the magnitude of the impairment observed on the total recall and delayed recall trials of the ISLT was consistent with the magnitude of impairment expected to occur. It is sensitive to the episodic memory impairment that characterizes MCI with high amyloid (unpublished data from the Australian Imaging, Biomarker & Lifestyle Flagship Study of Ageing study). Data are robust across different groups of healthy older individuals, and accordingly criteria used for defining abnormal performance are reliable (Thompson, et al., 2011; Lim, et al., 2012a; Lim, et al., 2012b). Data computations indicate that the ISLT will be sensitive to the expected changes in amyloid-related memory dysfunction with elenbecestat (E2609) treatment.

9.2.4 Rationale for Biomarkers

The biomarker strategy for this study includes the following aims:

- To determine whether elenbecestat (E2609) is superior to placebo on brain amyloid levels at 24 months as measured by amyloid PET in subjects with EAD
- To determine whether elenbecestat (E2609) is superior to placebo on CSF t-tau and p-tau levels at 24 months in subjects with EAD
- To determine whether elenbecestat (E2609) is superior to placebo on CSF A β levels at 24 months in subjects with EAD
- To determine whether elenbecestat (E2609) is superior to placebo on hippocampal atrophy at 24 months in subjects with EAD as measured by changes in hippocampal volume using vMRI
- To evaluate whether elenbecestat (E2609) is superior to placebo in preserving connectivity as measured by fMRI
- To explore the relationship between exposure (in CSF, plasma) of elenbecestat (E2609) with potential biomarkers of AD as deemed appropriate

CSF biomarkers and amyloid PET assessments on disease progression at 24 months (and at 12 months for amyloid PET) will be evaluated in a substudy of subjects. The CSF substudy is limited to a single timepoint at 24 months to acknowledge the additional burden to the

subject that a lumbar puncture procedure entails. Participation in the substudies is optional and will require specific consent.

These aims are discussed below in the context of the individual biomarker assessments to be used in this study.

Briefly, the biomarkers that will be utilized and assessed during this study are:

Soluble Biomarkers in CSF

A β (1-x) captures the effect on the total A β component; therefore, the measurement of this A β isoform most appropriately represents the total pharmacologic effect (A β [1-40] + A β [1-42] and other C-terminally truncated A β peptides such as A β [1-38]) on inhibition of BACE enzyme cleavage.

A β (1-42) measurements in CSF have shown high correlation with results using 11C-Pittsburgh Compound B (PiB), suggesting that CSF A β (1-42) reflects fibrillar A β content (Grimmer, et al., 2009). The aggregation of A β peptides into plaques, and subsequent retention of peptides in the brain parenchyma, accounts for reduced availability of A β to diffuse into the CSF. The decreases seen in AD due to amyloid plaque deposits are related to this decrease.

T-tau and p-tau are sensitive markers of axonal and neuronal degeneration (t-tau) and NFTs (p-tau), and have been demonstrated to increase in parallel with disease progression (Chintamaneni, et al., 2012).

Baseline levels of A β (1-42), t-tau, and p-tau and/or tau: A β (1-42) ratios will also help elucidate the extent of AD pathology at study entry, and can be combined with *ApoE4* genotype in addition to the baseline imaging variables to help explain differences in treatment response between subjects. (revised per Amendments 01 and 04)

Amyloid PET

Amyloid PET imaging will be performed in this study for 2 primary reasons: 1) as one of the methods of confirming the presence of amyloid pathology in the brain of subjects with EAD including MCI due to AD and the early stages of mild AD at study entry (the other method of confirming the presence of amyloid pathology is CSF assessment); and 2) to evaluate the effects of elenbecestat (E2609) on amyloid levels in the brain at 12 and 24 months. (revised per Amendment 04) This second part is an optional longitudinal substudy.

vMRI and fMRI

vMRI performed at 12 and 24 months will be used to evaluate the effects of elenbecestat (E2609) on rates of atrophy across the treatment groups and to provide support that effective treatment is associated with modification of disease progression. A large body of data has shown that structural MRI reliably tracks disease progression in AD. Atrophy tends to occur preferentially in the lateral temporal and posterior parietal regions during the early stages of disease and progresses towards the anterior regions of the brain (frontal cortex) in its later stages. For this reason hippocampal volume has been selected as a secondary endpoint, and

it is predicted that clinically efficacious doses will be associated with a slowing in the rate of hippocampal atrophy compared to rates observed in the placebo. Whole brain, ventricular volumes, and possibly other regions deemed to be of scientific value will also be measured.

Task free fMRI can be used to assess the integrity of functional networks within the brain to help determine effects of disease on brain function. fMRI eliminates performance confounds that are seen with task based functional neuroimaging. fMRI requires an additional 7 to 10 minutes of scan time for acquisition of the data. fMRI data will be used to generate connectivity maps based on critical anatomical regions (eg, precuneus, inferior frontal sulcus) which can then be used within subject to determine the effect of elenbecestat (E2609) on preserving connectivity known to degrade with progression of AD.

Exploratory Biomarkers

Exploratory biomarkers in plasma and CSF may be measured as validated assays (such as neurofilament light [NFL], neurogranin [Ng], or visinin like protein 1 [VILIP1]) become available. (revised per Amendments 02 and 03)

9.3 Selection of Study Population

Approximately 1330 subjects with EAD including MCI due to AD and the early stages of mild AD will be enrolled across up to approximately 350 centers worldwide. Randomization will be stratified according to region (7 levels), clinical dementia staging, with no more than approximately 25% of the randomized subjects diagnosed with the early stages of mild dementia due to AD, and concurrent AD medication use. (revised per Amendments 01 and 02) Subjects who do not meet all of the inclusion criteria or who meet any of the exclusion criteria will not be eligible to receive study drug.

9.3.1 Inclusion Criteria

Subjects must meet all of the following criteria to be included in this study:

1. MCI due to AD or Mild AD according to the National Institute of Aging – Alzheimer’s Association (NIA-AA) core clinical criteria and must have all of the following at Screening: (revised per Amendment 04)
 - a. MMSE score equal to or greater than 24
 - b. CDR global score of 0.5
 - c. CDR Memory Box score of 0.5 or greater
2. A history of subjective memory decline with gradual onset and slow progression over the last 1 year before Screening; this MUST be corroborated by a study partner
3. Cognitive impairment of at least 1 SD from age-adjusted norms in total recall or delayed recall on the ISLT.
4. Positive biomarker for brain amyloid pathology as indicated by at least 1 of the following:
 - a. PET assessment of amyloid imaging agent uptake into brain. Note: amyloid PET screens will be performed according to local regulatory guidelines and thus may be

restricted for those subjects who are not suitable for LP to obtain CSF for testing of eligibility.

b. CSF AD assessment (eg, $A\beta(1-42)$, tau: $A\beta(1-42)$ ratio) (revised per Amendment 04)

NOTE: Subjects may undergo both the amyloid PET and CSF assessments, but need a positive amyloid result in only 1 of the 2 procedures to confirm eligibility. Subjects who consent to amyloid PET or CSF for eligibility purposes are not required to participate in the amyloid PET or CSF longitudinal substudies. Use of a historical amyloid positive PET (conducted within 12 months before the planned date of randomization) is acceptable for determination of eligibility but will not suffice for the baseline assessment if the subject wishes to consent to the amyloid PET longitudinal substudy. (revised per Amendment 04) The historical imaging data must be made available to the sponsor.

5. Male or female subjects between 50 and 85 years of age, inclusive at the time of consent
6. If receiving an AChEI or memantine or both for AD, must be on a stable dose for at least 12 weeks prior to Randomization. Treatment-naïve subjects with AD can be entered into the study.
7. Subjects must have been on stable doses of all other (ie, non-AD related) permitted concomitant medications for at least 4 weeks prior to Randomization, except for medications which are administered as short courses (eg, up to 3 weeks unless discussed and agreed with Medical Monitor) of treatment (eg, anti-infectives, oral steroids) or which are to be used on a Pro re nata (PRN) basis. Subjects who require a short course of treatment, such as anti-infectives or oral steroids, may be randomized once the acute illness has completely resolved, even if the concomitant medication continues. (revised per Amendment 01)
8. Must have an identified study partner (defined as a person able to support the subject for the duration of the study and who spends at least 8 hours per week with the subject). The study partner must be literate and able to provide written informed consent. (revised per Amendment 04) In addition, this person must be willing and able to provide follow-up information on the subject throughout the course of the study. This person must, in the opinion of the investigator, spend sufficient time with the subject on a regular basis such that they can reliably fulfill the requirements of being a study partner. A study partner need not be living in the same residence with the subject. For such a study partner not residing with the subject, the investigator has to be satisfied that the subject can contact the study partner readily during the times when the study partner is not with the subject. Study partners need to provide input to the following assessments: CDR, FAQ, EQ-5D, QOL-AD, Zarit's Burden Interview, NPI-10, and the clinical assessment of suicidality. (revised per Amendment 01) Consideration can occur for the investigator to decide whether the study partner can provide information over the telephone or whether the study partner must attend the study visits in person with the subject.
9. Provide written informed consent. Subjects must, in the investigator's judgment, have the capacity to consent (capacity to consent should be determined in accordance with applicable professional standards and local laws/regulations). (revised per Amendment 04)

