- Physical examination or vital signs at Screening or Baseline which in the opinion of the investigator require further investigation or treatment or which may interfere with study procedures or safety. (revised per Amendment 04)

- Laboratory tests or ECG at Screening that in the opinion of the investigator require further investigation or treatment or may interfere with study procedures or safety. (revised per Amendment 04)
 - Other medical conditions (eg, cardiac, respiratory, gastrointestinal, psychiatric, renal disease) which are not adequately and stably controlled, or which in the opinion of the investigator(s) could affect the subject's safety or interfere with the study assessments (revised per Amendment 02)
 - Illiteracy, or severe visual or hearing impairment that would prevent the subject from performing psychometric tests accurately (revised per Amendment 01)
14. A prolonged QTc interval calculated using Fridericia's formula (QTcF) interval (QTcF greater than 450 ms according to central reading at Screening). (revised per Amendment 04) If the QTcF is greater than 450 ms on the first single 12-lead ECG, 2 additional 12 lead ECGs will be performed 1 minute apart and the mean of the 3 QTcF values will be calculated.
15. Malignant neoplasms within 5 years of Screening (except for basal or squamous cell carcinoma in situ of the skin, or localized prostate cancer in male subjects with treatment cycles completed at least 6 months prior to screening). Subjects who had malignant neoplasms but who have had at least 5 years of documented uninterrupted remission before Screening need not be excluded. (revised per Amendment 01)
16. Hypopigmentation conditions (eg, albinism and vitiligo). Hypopigmentation associated with scarring need not be exclusionary
17. Known or suspected history of drug or alcohol abuse or dependence within 2 years before Screening
18. Taking prohibited medications
19. Have participated in a clinical study involving:
- any therapeutic monoclonal antibody, protein derived from a monoclonal antibody, immunoglobulin therapy, or vaccine within 6 months before Screening for whom it cannot be documented that they were randomized only to placebo or never received study drug
 - elenbecestat (E2609)
 - any new chemical entity for AD with last study drug dose occurring within 6 months prior to Screening unless it can be documented that the subject received only placebo

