9.4.7 Prior and Concomitant Therapy

Any medication (including over-the-counter medications) or therapy administered to the subject prior to the study (within 6 months of randomization) and during the study (starting at the date of informed consent) will be recorded on the Prior & Concomitant Medication eCRF or Non-Pharmacological Procedures eCRF. The investigator will record on the Adverse Event eCRF any AE for which the concomitant medication/therapy was administered. If the concomitant medication/therapy is being administered for a medical condition present at the time of entry into the study, the investigator will record the medical condition on the Medical History and Current Medical Condition eCRF.

Listings of prohibited and permitted drugs are provided in [Appendix 2](#) (Prohibited medications are presented in [Listing 1](#), [Listing 2](#), and [Listing 3](#). Medications that are permitted with restrictions are listed in [Listing 4](#), [Listing 5](#), and [Listing 6](#)).

The following agents are not permitted before randomization (specific time frames are shown below) and until the last visit during the treatment period: (revised per Amendment 02)

- a) Immunoglobulin therapy and biologic drugs are not permitted within 6 months before Screening and until the last visit during the treatment period (revised per Amendment 02)
- b) Systemic immunosuppressive or immunomodulatory drugs are not permitted for a period of 5 half-lives or 60 days (whichever is longer) before randomization and until the last visit during the treatment period (revised per Amendments 02 and 04)
- c) Moderate to strong inhibitors of carboxylesterase 2 (CES2) enzyme activity are not permitted for a period of 5 half-lives or 7 days (whichever is longer) before randomization and until the last treatment visit. Simvastatin use is permitted only with QD evening administration.
- d) Live/live attenuated vaccines are not permitted within 3 months before randomization and until the last treatment visit (this does not apply to non-live/inactivated vaccines) (revised per Amendment 02)

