Appendix 2 List of Permitted and Prohibited Prior/Concomitant Medications

Prohibited medications are shown in [Listing 1](#), [Listing 2](#), and [Listing 3](#). Medications permitted with restrictions are listed in [Listing 4](#), [Listing 5](#), and [Listing 6](#). These may not be all-inclusive listings. Please contact the medical monitor(s) if the investigators have any questions or concerns regarding any medication not listed that your subjects may be taking before enrollment or start during the course of the E2609-G000-301 study.

Antibiotics, analgesics, and anti-inflammatory drugs intended for short courses of treatment are permitted and do not need to follow the restrictions of [Listing 6](#) for a stable dose of 4 weeks before Baseline. If these medications may affect cognitive function but the medications are clinically indicated, then cognitive testing should not take place until at least 72 hours after the last dose of the course of treatment.

Prohibited Prior/Concomitant Medications

Listing 1 Prohibited Medications Within 5 Half Lives or 7 Days, Whichever is Longer, Before Randomization and Until the Last Visit During the Treatment Period

Moderate to Strong Inhibitors of Carboxylesterase 2 (CES2) Enzyme Activity
Generic name
Loperamide
Orlistat
Telmisartan
Fenofibrate
Carvedilol
Manidipine
Diltiazem
Verapamil
Itraconazole (revised per Amendment 04)

NOTE: Simvastatin use is permitted only with once daily evening administration.

Listing 2 Prohibited Medications Within 5 Half Lives or 60 Days, Whichever is Longer, Before Baseline and Until the Last Visit During the Treatment Period

Systemic Immunosuppressants^a and Immunomodulatory Drugs (revised per Amendments 02 and 04)	
Prednisolone	Deltasone, Prednicot, Prednisone Intensol, Rayos, Sterapred, Sterapred DS
Methylprednisolone	Medrol, Meprolone
Dexamethasone	Decadron, Dexasone, Diodex, Hexadrol, Maxidex
Azathioprine	Azasan, Imur
Mycophenolate	CellCept, Myfortic
Fingolimod	Gilenya
Methotrexate	Trexall
Ciclosporine	Gengraf, Neoral

Prohibited Medications Within 6 Months Before Screening and Until the Last Visit During the Treatment Period (revised per Amendment 02)

Immunoglobulin Therapy and Biologic Drugs (revised per Amendment 02)	
Ranibizumab	Lucentis
Bevacizumab	Avastin
Infliximab	Remicade
Etanercept	Enbrel
Adalimumab	Humira
Omalizumab	Xolair
Efalizumab	Raptiva

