Immune globulin IV, IVIG, IGIV	Carimune, Flebogamma, Gamimune N, Gammagard, Gamunex, Gammar-P IV, Iveegam, Octagam, Panglobulin, Vigam, Polygam S/D, Privigen, Sandoglobulin, Venoglobulin-S
Denosumab	Prolia (revised per Amendment 02)
Other monoclonal antibodies not listed here	

^a Topical, ocular, and inhaled formulations with minimal systemic exposure need not be prohibited. (revised per Amendment 04)

Listing 3 Prohibited Live/Live Attenuated Vaccines Within 3 Months Before Randomization and Until the Last Visit During the Treatment Period (this does not apply to non-live/inactivated vaccines)

Bacterial vaccines	Viral vaccines
Bacillus Calmette-Guérin vaccine against tuberculosis	Measles vaccination
Typhoid vaccination (oral)	Mumps vaccination
Cholera vaccination (oral)	Rubella vaccination
	Oral polio vaccination (Sabin)
	Yellow fever vaccination
	Varicella (chickenpox) vaccination
	Rotavirus vaccination
	Japanese encephalitis vaccination
	Live attenuated influenza vaccine (FluMist in the United States and Canada, and Fluenz in Europe)

This list is not exhaustive

Permitted Prior/Concomitant Medications

Listing 4 Medications Which Need To Be on a Stable Dose for 12 Weeks Before the Cognitive Assessments at Visit 2 and Should Remain on the Same Stable Dose From Visit 2 to Follow Up Visit 15

Cognitive Enhancers	
Donepezil	Aricept
Rivastigmine	Exelon
Galantamine	Reminyl
Memantine	Namenda

Listing 5 Permitted Medications Used on PRN Basis Which Are Not to be Used Within 72 Hours Before Cognitive Testing

Generic name	Trade name
Opiates	
Morphine	Astramorph PF, Avinza, Depo Dur, Duramorph, Infumorph, Kadian, MS Contin, MSIR, Oramorph SR, RMS, Roxanol
Opiate Agonists	
Meperidine	Demerol, Meperitab
Fentanyl	Actiq, Duragesic, Fentora, Onsolis, Sublimaze
Codeine	Codeine
Oxycodone	Dazidox, Endocodone, Eth-OxyDose, OxyContin, OxyFast, OxyIR, Percolone, Roxicodone, Roxicodone Intensol
Other opioids or opioid agonists which are used on PRN basis	
Benzodiazepines (short-term use only, [ie, 2 to 4 weeks]) and sedatives (revised per Amendment 04)	
Estazolam	ProSom
Alprazolam	Alprazolam Intensol, Niravam, Xanax
Triazolam	Halcion
Midazolam	Versed
Lorazepam	Ativan
Flunitrazepam	Rohypnol
Temazepam	Restoril
Clonazepam	Ceberclon, Klonopin
Diazepam	Diastat, Dizac, Valium
Chlordiazepoxide	H-Tran, Librium
Flurazepam	Dalmane
Zopiclone	(various)
Zolpidem	Ambien; others
Ramelteon	Rozerem
Amitriptyline	(various)
Dothiepin	(various)
Risperidone	Risperdal
Olanzapine	Zyprexa

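### In the Amendment 04 text, inclusion criterion 7 allows randomisation during a continuing oral steroid course, while Section 9.4.7(b) and Listing 2 prohibit systemic steroids for at least 60 days beforehand and throughout treatment

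*Protocol*

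**What the plan says.** References are to the Amendment 04 text (Version 5.0) unless stated otherwise.

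**The permission.** Section 9.3.1, item 7, asks for 4 weeks of stable dosing of other permitted medications before randomisation. It excepts short courses, with an example limit of 3 weeks, and gives oral steroids as one of its two examples. Its second sentence goes further: subjects who require a short course, "such as anti-infectives or oral steroids, may be randomized once the acute illness has completely resolved, even if the concomitant medication continues". Section 9.4.7 repeats the short-course exception with the same example. The synopsis carries both texts.

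**The prohibition.** Section 9.4.7(b) states: "Systemic immunosuppressive or immunomodulatory drugs are not permitted for a period of 5 half-lives or 60 days (whichever is longer) before randomization". The ban then runs to the last visit of the Treatment Period. Listing 2 in Appendix 2 names prednisolone, methylprednisolone and dexamethasone, and prohibits them "Within 5 Half Lives or 60 Days, Whichever is Longer, Before Baseline and Until the Last Visit During the Treatment Period". Its footnote gives the only exemption: "Topical, ocular, and inhaled formulations with minimal systemic exposure need not be prohibited". Exclusion criterion 18 in Section 9.3.2 reads, in full, "Taking prohibited medications", and Section 9.3 adds that subjects "who meet any of the exclusion criteria will not be eligible to receive study drug".

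**A third text.** The introduction to Appendix 2 also speaks of short courses, and covers antibiotics and analgesics as well. Of its third class it says: "anti-inflammatory drugs intended for short courses of treatment are permitted and do not need to follow the restrictions of" one of the listings. The listing named there is Listing 6, and the rule lifted is its requirement "for a stable dose of 4 weeks before Baseline".

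**The concern.** A subject who is finishing an oral prednisolone course at Visit 2, with the acute illness resolved, is expressly allowed in by inclusion criterion 7. The same subject is taking a drug that Listing 2 prohibits, and so meets exclusion criterion 18. A site working from Section 9.3.1 would randomise; a site working from Appendix 2 would not. With up to approximately 350 sites, uneven application is foreseeable.

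The stake is eligibility and safety. Listing 2 classes these drugs as systemic immunosuppressants. Section 7.1 reports some reduction in CD4 lymphocyte counts by Day 15 in the multiple-dose study at 50 to 100 mg, a range that includes this trial's 50 mg dose. Section 9.3.3 requires study drug to be interrupted for confirmed Grade 2 or greater lymphocytopenia and for severe infection. Starting study drug during a systemic steroid course is the overlap that the 60-day rule exists to prevent.

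**Working it through.** There is no sample size, power or alpha figure to reproduce. The check sets the rules side by side and looks for a text that reconciles them.

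| Rule | Applies to oral steroids because | Steroid-free time before randomisation | After randomisation |
|---|---|---|---|
| Inclusion 7 (9.3.1; synopsis) | named as an example | 0 days: the course may continue | use implied, since the course continues |
| Short-course sentence (9.4.7; synopsis) | named as an example | no 4-week stable dose needed | silent |
| 9.4.7(b) | Listing 2 supplies the drug names | at least 60 days | prohibited to last treatment visit |
| Listing 2 | three corticosteroids named | at least 60 days | prohibited to last treatment visit |
| Exclusion 18 | through the prohibited listings | no window of its own | not stated |

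1. **Same reference point.** Section 9.4.7(b) counts back from randomisation and Listing 2 from Baseline. Subjects are randomised at Visit 2 (Day 1), where the baseline assessments are also done, so both windows end on the same day.

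2. **Does the route exemption help?** No. It covers topical, ocular and inhaled forms, and inclusion 7 speaks of oral steroids.

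3. **Does the word *permitted* in inclusion 7 help?** It qualifies the stable-dose requirement in the first sentence. The second sentence separately authorises randomisation on a continuing course and names oral steroids.

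4. **Does the Appendix 2 introduction help?** It calls short-course anti-inflammatory drugs permitted, but it names neither steroids nor Listing 2. The only restriction it expressly waives is the Listing 6 stable-dose rule. It leaves the conflict unsettled.

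5. **Size of the gap.** 60 − 0 = 60 days at least. The 5-half-lives arm can only lengthen this.

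6. **Operational meaning.** Section 9.1.1 gives a prerandomisation phase of up to 50 days, plus up to 30 more if required.
   - 60 − 50 = 10 days, so under the 60-day rule any steroid dose taken after consent pushes randomisation past the standard phase.
   - 50 + 30 = 80 and 80 − 60 = 20, so the wait fits the extended phase only if the last dose falls within 20 days of consent. Otherwise the subject must be rescreened or is excluded.
   - Inclusion 7 asks for no wait once the illness has resolved.

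7. **Extent of the permissive wording.** Oral steroids appears twice in inclusion 7, once in the 9.4.7 short-course sentence, and correspondingly twice and once in the synopsis: 2 + 1 + 2 + 1 = 6.

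8. **Which versions.** Inclusion 7 has the same permission in the Amendment 03 text. In the text carrying Amendment 05 changes, Listing 2 has the same ban, but the inclusion criteria and Section 9.4.7 are not in the part supplied.

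**The case against.** The best case for the protocol is that the permission is deliberate and specific. Short-course oral steroids are named in inclusion 7 and in 9.4.7, and again in the synopsis, and that wording is tagged to Amendment 01. Inclusion 7 attaches conditions: a short course and full resolution of the illness. Exclusion criterion 12 targets chronic inflammatory disease that needs systemic immunosuppression. A site could fairly read inclusion 7 as the exception and Listing 2 as the general rule, leaving only a missing cross-reference. That reading is tenable as intent, but the protocol states no such precedence. Section 9.4.7(b) was revised at Amendments 02 and 04 without any exception for short oral courses.

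A reader might infer three stronger things that the documents do not support.

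- **That all the rules together yield one answer, not eligible, so inclusion 7 is simply an error.** Section 9.3 points that way, but four permissive places and the Appendix 2 introduction point the other. The document does not show which was meant.
- **That exclusion criterion 18 itself imposes the 60-day ban.** It names no drug and no window; both come from 9.4.7(b) and Listing 2.
- **That subjects on 50 mg face a demonstrated infection risk.** Section 7.1 ties its statement on relapse of herpes and other infections to 200 and 400 mg, where counts fell close to or below the lower limit of normal. Entry also requires a lymphocyte count at or above that limit, and haematology is drawn at every visit. The safety argument is precautionary.

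The version objection also stands in part: text after Amendment 05 may already differ.

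**Conclusion.** The point holds for the Amendment 04 text as a contradiction between two explicit rules: 0 days against at least 60 days steroid-free before randomisation, and continued use against a ban through treatment. It concerns oral steroids only and does not extend to anti-infectives. It is worth correcting because it governs an entry decision and the remedy is a few words.

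It rests on reading Listing 2 as defining the drugs covered by 9.4.7(b), which Section 9.4.7 supports by referring to the listings for prohibited medications. Whether inclusion 7 still reads this way after Amendment 05 cannot be confirmed from the part supplied, although its identical wording at Amendments 03 and 04 makes that plausible. The number of subjects affected is not given. A reader might look for a consequence for type I error, power or the estimated effect; nothing in the protocol supports one and none is claimed.

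**What to change.** Make the two rules agree in one of two ways.

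- **(a) Let the 60-day rule govern.** Delete oral steroids from inclusion 7 and from the 9.4.7 short-course sentence, and from their synopsis copies (six occurrences). This is the more cautious option. The cost is a small edit and a memo to sites; a few subjects will wait, be rescreened or be excluded.
- **(b) If short courses are intended, as the Amendment 01 wording suggests, say so where the ban is written.** Add to 9.4.7(b) and Listing 2 an explicit exception for short oral steroid courses, with a maximum duration and a stated washout before the first dose, and align inclusion 7 with it. The cost is a clinical decision on the washout and a slightly longer edit.

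The sponsor should apply the change to the Amendment 05 text if inclusion 7 is unchanged there. Under option (b), Listing 2 in that text would need the exception too, since it carries the same ban.
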